### 3.D WITHDRAWAL CRITERIA

Reasons for **premature discontinuation of the allocated management strategy** include:

- Patient moving for long term stay in a medicalised nursing home,
- Any lack of compliance to the study procedures which can compromise the study progress, and, in particular, for the Intervention group only:
  - a) Absence of phone call to the study vocal server to report clinical status for more than 1 month for another reason than being away from home,
  - b) Refusal or inability to follow the four individual home education sessions before Visit 1 as detailed in section 4.B.3.1.

Whenever possible, in case of premature discontinuation of the allocated management strategy, patients will be followed up until Month 12 as initially planned (*by regular visits at the investigational centre and standardised phone interviews, as detailed in section 4.B.3.2*).

Reasons for **study premature withdrawal** include:

- Patient moving away from the geographic area of the investigational centre resulting in the patient's inability to attend study visits,
- Withdrawn consent as described in the Patient Informed Consent,

- Death.

The reason, date and time for premature discontinuation of the allocated management strategy and/or study premature withdrawal will be recorded in the electronic Case Report Forms (e-CRF) of the patients concerned by their investigator. Survival data until Month 12 will be collected unless the patient disagrees.

**The patient will be replaced** only if premature discontinuation of the allocated management strategy or study premature withdrawal occurs before the end of Visit 1 (*see section 4.B.3.1*).

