#### **During Visit 0, the investigator will:**

- Perform a physical examination including vital signs, pulse oximetry, height and weight,
- Randomise the patient (*see section 4.B.2*),
- Schedule an appointment for Visit 1, five (5) weeks ( $\pm 5$  days) after Visit 0,
- Schedule all medical evaluations and laboratory samplings to be performed between Visit 0 and Visit 1,
- Provide the patient with the “Patient’s Study Diary”\*,

- Send a standardised education request form to the health counsellor and provide the patient with a fulfilled written action plan (*for patients randomised to the Intervention group only*).

\* "Patient's Study Diary" contains the following: schedule of planned contacts (*visits at the investigational centre, phone interviews, and for patients in the Intervention group, education sessions*); investigator's name and telephone number, and all useful contacts; weekly forms for the patient to record any use of health care services (*medical and paramedical consultations, attendances at emergency departments, hospitalisations*); and, for patients of the Intervention group only, space to report the date and results of their home respiratory self-assessments (*SpO2, pulse rate, FEV1 and body temperature as detailed in sections 5.A.1.2 and 5.A.4*).

**During Visit 0**, for each eligible patient, the investigator will record the following data in the e-CRF:

- Date of Visit 0 and date of signature of Patient Informed Consent,
- Date of birth, sex, height and weight,
- Results of the physical examination including vital signs (*i.e., systolic and diastolic blood pressures*) and pulse oximetry (*pulse rate and SpO2*) on room air and also, only for patients on oxygen therapy, on oxygen,
- Social conditions (*civil status, area of residence and type of residence*),
- COPD history including:
  - ✓ Date of diagnosis and suspected cause of COPD,
  - ✓ Smoking status and history (*i.e., current or ex-smoker, the later being defined as patients who have stopped smoking for at least 6 months prior to Visit 0, current number of cigarettes smoked per day, estimated number of pack-years, smoking start and stop dates, if applicable*),

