## COPD EDUCATION

**Patients randomised in the Control group** will receive the usual COPD education as per investigational centre routine practice. The content and modalities of each centre will be collected before study initiation, as well as any modifications throughout the study period, if applicable.

**Patients randomised in the Intervention group** will undergo four (4) individual home education sessions, performed on a weekly basis by a community-based health professional (*called for the study 'health counsellor' and detailed in section 5.A.1*):

- The four sessions will be performed before Visit 1, in a minimum of 3 weeks and a maximum of 5 weeks after randomisation.
- Each individual session is planned to last 60 to 90 minutes during which the health counsellor will use specific teaching material in local study language and will give the patient the printed education documents (*handbooks and brochure, as detailed in section 5.A.1.1*) and the study medical devices (*portable pulse oximeter, spirometer and thermometer, as detailed in section 5.A.4*). The patient will also be trained to perform phone calls to the study dedicated vocal server. After each education session, the understanding and skills of the patient will be assessed and a report will be sent by the health counsellor to the investigator concerned.

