## **VISITS AT THE INVESTIGATIONAL CENTRE (*VISITS 2 TO 5*)**

**Visits 2 to 5** are scheduled at Month 3, Month 6, Month 9 and Month 12 from Visit 1, respectively. These visits may vary from their planned timelines starting at Visit 1 by  $\pm 30$  days, without modifying the initially planned timelines of the following visits if a given visit needs to be advanced or postponed.

**During Visits 2 to 5**, the investigator will record the following data in the e-CRF:

- Date of Visit,
- Results of the physical examination including vital signs (*i.e.*, *systolic and diastolic blood pressures*), weight and pulse oximetry (*pulse rate and SpO2*) on room air and also on oxygen for patients on oxygen therapy,
- Changes in social conditions, if applicable,
- Changes in smoking status, if applicable,
- Recovery from concomitant diseases since the last visit, if applicable,
- Changes in COPD and non-COPD medication, including oxygen therapy, CPAP, Non-Invasive Ventilation and vaccines (*as detailed in section 5.D*), since the last visit, if applicable,
- Occurrence of COPD exacerbations (*as defined in section 6.A.2.2*) since the last visit,
- Occurrence of other Adverse Events (*see section 6.B*) since the last visit,
- For patients on oxygen therapy, checking of the *NOWOX* device (*to detect the need for an exchange or return of the device at study end*), and, if applicable, the reason for exchanging or returning the *NOWOX* device and the serial number of the new *NOWOX* device assigned, whenever necessary; of note, patients starting oxygen therapy during their study participation will be given a *NOWOX* following the procedure described in section 4.B.3.1 and their start date and criteria for oxygen prescription will be collected, as described in section 4.B.1.2.
- Use of health care services (*see section 6.A.2.3*) since the last visit.

**At Visit 3 (Month 6) and Visit 5 (Month 12 or study end in case of premature withdrawal)**, additional questionnaires and examinations will be performed as follows:

- The SGRQ-C, 15D and HADS questionnaires (*as detailed in sections 6.A.2.4 and 6.A.2.7 and provided in Appendix 3*), self-administered before the consultation with the investigator at **Visit 3 (M6)** and **Visit 5 (M12)**,
- Assessment of the severity of dyspnoea using the modified Medical Research Council Dyspnoea Scale at **Visit 5 (M12)**,
- Comorbidities to allow the calculation of the Charlson Comorbidity Index at **Visit 5 (M12)**,

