### **7.B.3**     *Statistical methodology*

#### **7.B.3.1.**   Data sets analysed

Two (2) different analysis data sets are foreseen. They will be exhaustively defined prior to the database lock (*see section 4.B.4*):

- Full Analysis data Set (*FAS or extended safety data set*), composed of all randomised patients having entered the *Run-In Period (starting at Visit 0, as defined in section 4.B.3.1)*. This FAS will be used for description of dropouts, and extended evaluation of safety,
- Intention To Treat (ITT) data set, which will be the subset of the FAS, composed of all randomised patients having entered the *Follow-Up Period (starting at the end of Visit 1, as defined in section 4.B.3.2)*. This ITT data set will be used for description at Selection, and evaluation of efficacy, safety and medico-economic parameters.

If prior to the database lock (*see section 7.A*), it appears necessary to define a secondary Per Protocol (PP) data set, which would be a subset of the ITT data set, composed of all randomised patients who have no major protocol deviations throughout their study period, this PP data set would be used for the secondary supportive analysis of the primary efficacy criterion and check of its robustness. For example, if it appears that 25.0% or more of the patients from the ITT data set have prematurely discontinued their allocated COPD management strategy and completed the study as initially planned (*as described in section 3.D*), a secondary supportive analysis of the primary efficacy criterion would be added comparing the recorded average yearly duration of unscheduled hospitalisations whatever their reason, between three (3) groups: *i*) patients from the Intervention group having completed the study as planned, *ii*) patients from the Intervention group having prematurely discontinued the evaluated Home-Based Disease Management Program without being prematurely withdrawn from the study and *iii*) patients from the Control group.

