#### 7.B.3.3. Handling of dropouts and missing data

The number and percentage of patients prematurely withdrawn from the study after their randomisation will be provided by study group (*and globally*) for all randomised patients (*i.e., on the FAS defined in section 7.B.3.1*), as well as for the subgroup of randomised patients having entered the *Follow-Up Period* (*i.e., on the ITT data set defined in section 7.B.3.1*). All withdrawn patients after randomisation will be further described by study group (*and globally*) regarding their time to dropout and reason for premature withdrawal. Particular attention will be paid to the description of Adverse Events (*either serious or not serious, according to their regulatory definition provided in section 8.A*) leading to study premature withdrawal, as detailed in section 7.B.3.7.

Time to dropout for any reason (*expressed in number of days*) throughout the *Follow-Up Period* will be described by study group, on the ITT data set, using Kaplan-Meier's estimates. It will be compared between both study groups with the Log rank test.

Moreover, time to death whatever its associated diagnosis (*expressed in number of days*) throughout the *Follow-Up Period* will be described by study group, on the ITT data set, using Kaplan-Meier's estimates. If relevant, it will be compared between both study groups with the Log rank test.

If relevant, the handling of missing data and/or mistimed evaluations will be described in the statistical analysis plan approved prior to the database lock. Whenever needed, the most pragmatic approach will be used to extrapolate missing information according to the Intention To Treat principles.

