In the subgroup of patients on oxygen therapy at Selection and/or during their study participation and on the period of their oxygen prescription overlapping their holding of the *NOWOX* device, the average daily duration prescribed will be tabulated by study group. For each patient for whom a change in the daily duration of oxygen prescription is recorded throughout the *Follow-Up Period*, the individual daily duration of oxygen prescription will be estimated by using the sum of all recorded daily durations prescribed multiplied by the number of days of the corresponding prescription, divided by the total number of days on oxygen therapy. In case of missing or incomplete information necessitating monthly approximation in this average calculation, it will be considered that each month lasts 30.5 days.

**Compliance to oxygen therapy:** in the subgroup of patients on oxygen therapy at Selection and/or during their study participation and on the period of their oxygen prescription overlapping their holding of the *NOWOX* device, the average daily use of oxygen therapy over 24 hours, as well as the average use of oxygen therapy at night (*i.e., over the time interval [22:00 ; 6:00]*) and the average use of oxygen therapy during the day (*i.e., over the time interval [06:00 ; 22:00]*) will be calculated separately over at most eight (8) successive periods (*for the first patients included in the study who have been followed up 24 months*) defined by the scheduled visits of the patients at the investigational centre, without taking into account the recordings collected by the *NOWOX* device on the day of each actual visit, *i.e.,* when applicable, over the successive periods:

- between the day following the actual date of Visit 1 and the day preceding the actual date of Visit 2 (*both included*) (*period 1*),
- between the day following the actual date of Visit 2 and the day preceding the actual date of Visit 3 (*both included*) (*period 2*),
- ... and so on, up to the last period between the day following the actual date of Visit 8 and the day preceding the actual date of Visit 9 (*both included*) (*period 8, if applicable*).

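### The planned survival curve and log-rank test start at Visit 1, not at randomisation, so deaths in the Run-In fall outside the only comparison of time to death

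*Protocol*

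**What the plan says.** **The analysis.** Protocol 7.B.3.3 fixes the set and window for time to death in these words: "whatever its associated diagnosis (*expressed in number of days*) throughout the *Follow-Up Period* will be described by study group, on the ITT data set". The method is Kaplan-Meier estimation. A log-rank comparison follows if judged relevant.

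**The set.** Protocol 7.B.3.1 defines the ITT data set as one "which will be the subset of the FAS, composed of all randomised patients having entered the" Follow-Up Period, which begins at the end of Visit 1. The same section defines the FAS as all randomised patients who entered the Run-In, which starts at Visit 0. The FAS is used for describing dropouts and for extended safety.

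**The gap.** Randomisation takes place at Visit 0 (4.B, 4.B.1.2). The Run-In lasts 5 weeks ± 5 days, exceptionally up to 4 weeks more (4.B.3.1).

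**What happens in the gap.** At Visit 0 the investigator must "provide the patient with a fulfilled written action plan (*for patients randomised to the Intervention group only". For the Intervention arm's home education, 4.B.3.1 says: "The four sessions will be performed before Visit 1, in a minimum of 3 weeks and a maximum of 5 weeks after randomisation".

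**Replacement.** Section 3.D lists death as a reason for study withdrawal and replaces a patient "only if premature discontinuation of the allocated management strategy or study premature withdrawal occurs before the end of Visit 1".

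**The concern.** Reaching the end of Visit 1 is an event after randomisation, and the two arms reach it after about five weeks of different care. A patient who dies in the Run-In is neither an event nor at risk in the planned survival analysis. Any early effect on mortality, in either direction, would be outside the curve and the test. The label ITT may also lead a reader to take the curve as a comparison of all randomised patients.

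Death matters to how the trial is read. Excess death in the Intervention arm would change the meaning of fewer hospital days. Section 1.C says survival will be evaluated, and 6.C.2 names the number of deaths as an outcome for cost-effectiveness. An all-randomised set already exists in the plan and is not used for this comparison.

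**Working it through.** **Step 1. Where a Run-In death appears in the plan**

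| Planned output | Includes Run-In deaths? | Curve or test between arms? |
|---|---|---|
| Time to death, 7.B.3.3 | No (ITT set, Follow-Up Period) | Curve; log-rank if relevant |
| Time to dropout, Kaplan-Meier, 7.B.3.3 | No (ITT set, Follow-Up Period) | Curve and log-rank |
| Time and reason of all withdrawals after randomisation, 7.B.3.3 | Yes, with later deaths, by arm | No |
| Run-In safety tables on the FAS, 7.B.3.7 | Yes, by arm | No; tests are ruled out |
| SAE summaries over both periods, separately and globally, 7.B.3.7 | Yes, within SAEs, by arm | No |
| Individual SAE listings timed from Visit 0, 7.B.3.7 | Yes, by arm | No |
| Cost-effectiveness ratio on deaths, 7.B.3.6 | No (ITT set, Follow-Up Period) | Difference in deaths, only if costs differ significantly |

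Run-In deaths are therefore in the report, but no survival curve or test includes them.

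**Step 2. How many deaths this could be**

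The protocol states no mortality figure, so there is none to reproduce.

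Inputs from the protocol:
- n = 153 per arm (7.B.2: 143 / (1 − 0.0625) = 152.5, rounded up to 153).
- Run-In R = 35 days, with 30 to 40 days as the planned tolerance.
- Follow-Up H = 365 days. For the group described in 7.B.3.5 as "for the first patients included in the study who have been followed up 24 months", H = 730 days.

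Assumptions, not in the protocol:
- Mortality m in the 12 months after Visit 1 of 8%, 12% or 18%.
- A constant hazard from randomisation.

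Formulas:
- λ = −ln(1 − m) / 365
- Run-In deaths per arm = 153 × (1 − exp(−λR))
- Follow-Up deaths per arm = 153 × exp(−λR) × (1 − exp(−λH))
- Share left out = Run-In deaths / (Run-In deaths + Follow-Up deaths)

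Worked example, m = 8%, R = 35, H = 365: λ = 0.08338 / 365 = 0.0002284. Run-In deaths = 153 × 0.00796 = 1.22. Follow-Up deaths = 153 × 0.9920 × 0.08 = 12.14. Share = 1.22 / 13.36 = 9.1%.

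| | m = 8% | m = 12% | m = 18% |
|---|---|---|---|
| Run-In deaths per arm, R = 35 | 1.22 | 1.86 | 2.88 |
| All deaths per arm to Month 12 | 13.36 | 20.00 | 29.90 |
| Share left out, R = 35, H = 365 | 9.1% | 9.3% | 9.6% |
| R = 30, H = 365: deaths; share | 1.04; 7.9% | 1.60; 8.1% | 2.48; 8.4% |
| R = 40, H = 365: deaths; share | 1.39; 10.3% | 2.13; 10.5% | 3.29; 10.9% |
| Share left out, R = 35, H = 730 | 5.0% | 5.2% | 5.5% |

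The share does not depend on n. As a cross-check, the Run-In is 35 / (35 + 365) = 8.8% of planned time after randomisation.

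The number of patients followed to Month 24 is not given. If they are 25% of patients, the pooled share is 7.5-8.1%; if 50%, it is 6.4-7.0%. Extended Run-Ins are exceptional and are not counted here.

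**The case against.** The strongest case against the point has four parts.

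- **Run-In deaths are already visible.** This stands. A reader might infer that these deaths are lost, or are never shown with later ones. The documents do not support that. Section 7.B.3.3 describes all withdrawals after randomisation by arm, time and reason on the FAS, and 7.B.3.7 summarises SAEs over both periods and lists each one from Selection. What is missing is narrower: a survival curve, and any test, on the groups as randomised. The withdrawal description may also miss deaths that follow a live withdrawal.
- **No bias is shown.** This stands too. A reader might infer that the planned comparison is biased. Leaving out Run-In deaths distorts it only if those deaths differ between arms, and nothing in the protocol indicates that they would. The weekly telephone follow-up belongs to the Follow-Up Period, so only part of the intervention is active in the Run-In. The constant hazard is also open to question: patients with expected survival under 6 months are excluded (3.C), while inclusion at hospital discharge is foreseen (4.B.3.1).
- **The analysis is exploratory.** Section 7.B says all results other than the primary analysis are descriptive and carry no causal reading, and 1.C expects no significant survival benefit. This lowers the weight. It does not make a conditional comparison the better choice for checking a harm.
- **Set and window match the primary criterion.** They do, and that is a reason to keep the planned curve as a supportive display. Hospital days are counted in the Follow-Up Period by definition; death can be timed from randomisation.

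**Conclusion.** The point holds as a minor one. The planned time-to-death curve and its conditional log-rank test are restricted to patients who reached the end of Visit 1, although the arms are treated differently from Visit 0 and an all-randomised set is defined. The time-to-dropout test and the conditional cost-effectiveness ratio on deaths carry the same restriction.

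Under the assumptions above, about 1 to 3 deaths per arm are left out: about 9-10% of deaths to Month 12 with a 35-day Run-In, and about 5% for patients followed to Month 24. These figures measure what is omitted, not a bias. A difference between arms in these deaths is possible but not shown. The sample size and the primary analysis are unaffected, and no confirmatory conclusion rests on this comparison.

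**What to change.** In 7.B.3.3:

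- Describe time to death from the date of randomisation on the FAS, and apply any log-rank test to that set, labelled exploratory.
- Use all survival data collected under 3.D. Censor at the last date known alive or at the end of the patient's planned follow-up. Month 12 can be a common horizon for display without discarding Month 24 data.
- Keep the ITT/Follow-Up curve as a supportive display aligned with the primary criterion.

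The cost is one or two sentences and one more exploratory analysis. Run-In deaths need no new data: 3.D records the date and reason of each withdrawal, and 8.B starts adverse event reporting at Visit 0.

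The downside concerns patients withdrawn alive before Visit 1. Section 3.D says "Survival data until Month 12 will be collected unless the patient disagrees", but the follow-up visits "are scheduled at Month 3, Month 6, Month 9 and Month 12 from Visit 1, respectively", so Month 12 has no clear date for someone who never reached Visit 1. Such patients may be censored early unless 3.D also sets a survival date for them, for example one counted from randomisation.

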#### 7.B.3.4. Evaluation of protocol deviations

Prior to the database lock, all protocol deviations encountered throughout the study will be reviewed (*see section 4.B.4*) and their consequences on the efficacy evaluations performed will be evaluated. A deviation will be considered major when it is likely to bias significantly the interpretation of the efficacy results, especially the primary efficacy criterion (*i.e., the individual yearly duration of unscheduled hospitalisations whatever their reason*). All other protocol deviations will be considered minor.

A listing of all protocol deviations will be provided for all randomised patients (*i.e., on the FAS defined in section 7.B.3.1*), including the type (*major/minor*) of protocol deviations according to the decisions made. The number and percentage of patients with protocol deviations will be tabulated by study group (*and globally*) and type of protocol deviations on the Intention To Treat (ITT) data set (*defined in section 7.B.3.1*).

Protocol deviations which will be evaluated will include:

- deviations in inclusion and exclusion criteria,
- deviations in dates of visits and assessments times, including the cases of study premature withdrawals,
- deviations in the allocation and/or the performance of the study educational program.

#### 7.B.3.5. Evaluation of efficacy

The evaluation of efficacy will be performed by study group, on the Intention To Treat (ITT) data set (*defined in section 7.B.3.1*).

If it appears necessary to define a secondary Per Protocol (PP) data set (*as mentioned in section 7.B.3.1*), a listing highlighting all patients excluded from the PP data set and the reason(s) for their exclusion will be provided by study group, according to the decisions made prior to the database lock.

